18.2.1 Variables and derivations

Variables:

- All AEs and SAEs will be captured in the "Adverse Events" eCRF form.

Derivations:

- AE and SAE occurred between visit Baseline Visit 2 (week 0) and Visit 8 (week 24) will be used.

18.2.2 Analyses

Population: FAS and PP

Stratification: Table: Add the strata as needed in case subjects with dose modification exceeding 20% based on enrolled population as per section 7.3:

- a. Subjects on 1.5 mg only by Primary SOC and PT in decreasing order
- b. Subjects on 0.75 mg only by Primary SOC and PT in decreasing order

c. Subjects with any dose modification* by Primary SOC and PT in decreasing order

* Subjects who have received at least one dose of 1.5 mg and at least one dose of 0.75 mg

Statistics: The proportion of patients with at least one AEs, TEAEs, and SAEs occurring within the duration of the study (24 weeks) after being administered dulaglutide 1.5 or 0.75 mg will be presented followed by primary SOC and PT. Frequency, percentage and corresponding 95% confidence interval will be provided for table. 95% CI is calculated using exact binomial method (Clopper-Pearson method) for single proportions for the incidence of total adverse events and serious adverse events. Additionally, all the analysis will be repeated for the below mentioned subgroups:

- age (<65 year and \geq 65 year)
- HbA1c (<8.5 and \geq 8.5)
- Sex (Female and male)
- BMI category (<27 kg/m²) and \geq 27 kg/m²)

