9.6. Sample Size Determination

An estimated 250 participants will be screened, and assuming a 20% screen failure rate, an estimated 200 participants will be initiated on IP. Assuming a 20% dropout rate by the end of the study period, approximately 160 patients at the end of the study would allow for an adequate description of AEs and other safety outcomes. This is required to fulfill the market authorization clause.

10. Supporting Documentation and Operational Considerations

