7.4 Statistical tests

Unless otherwise specified, testing effect of dulaglutide on change from baseline will be conducted at a 2-sided alpha level of 0.05, and CIs will be calculated at 95%, 2-sided.

The mixed model for repeated measures method, Negative binomial models, and Cox proportional hazard models techniques will be used.

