Additionally, all the analysis will be repeated for the below mentioned subgroups:

- age (<65 year and \geq 65 year)
- HbA1c (<8.5 and \geq 8.5)

- Sex (Female and male)
- BMI category (<27 kg/m²) and \geq 27 kg/m²)

21. Other assessments

The listings will be presented for 12-Lead ECG data at screening using SAF population.

The Physical examination assessment will be presented in data listings and summarised as number and percentage (n and %) using SAF population. Physical examination data will be classified as normal and abnormal.

22. Revision history

Version	Date	Change
1.0	19-Dec-2022	Original Document
2.0	19-May-2023	
1. Updated Enroll Population Definition2. Added plots for the HbA1c analysis3. Updated primary and secondary analysis text for the 95% CI presentation in mock shells.4. Added plots vital sign parameters.

23. Appendix 1: Programming Conventions for Tables, Data Listings and Figures (TLFs)

Programs will be developed and maintained and output will be verified in accordance with current risk-based quality control procedures. Tables, figures, and listings will be produced with validated software. The production environment for statistical analysis consists of statistical analysis software; for example, the SAS System version 9.4 or later.

All percentages (%) for a specific summary are calculated using the total number of subjects included in the relevant analysis population as the denominator, unless otherwise specified.

Data listings will be based on all subjects, unless otherwise specified.

In general, if we have no response or record for respective parameter in data (i.e., n=0) then while presenting statistics in table only n will be presented as "0" and other statistics will be left blank. In case we have only one response or record for respective parameter (i.e., n=1) in data then statistic SD in table will be left blank.

By default, for continuous measures, summary statistics will include, unless otherwise specified:

- n
- Mean
- Median
- Maximum
- Minimum
- Standard error
- SD
- Frequency of Missing Values.

For categorical measures, summary statistics will include, unless otherwise specified:

- Frequency of non-missing values
- Percentage, and
- Frequency of Missing Values.

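### The primary 24-week AE proportion is a crude count with no allowance for the planned 20% dropout, and no analysis gives a follow-up-adjusted 24-week risk; the effect is small in the FAS and material only for common AEs in the safety population

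*SAP*

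**What the plan says.** The proportion of patients reporting AEs and SAEs from baseline to Week 24 is a primary endpoint (Protocol 3, SAP 3.1). SAP 18.2.2 summarises it as "The proportion of patients with at least one AEs, TEAEs, and SAEs occurring within the duration of the study (24 weeks", in the FAS and the per-protocol set. For total AEs and SAEs, "95% CI is calculated using exact binomial method (Clopper-Pearson method) for single proportions". SAP Section 23 (Appendix 1) sets the denominator: percentages "are calculated using the total number of subjects included in the relevant analysis population as the denominator". Nothing in 18.2.2 refers to length of follow-up.

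On numbers, Protocol 9.6 says that "an estimated 200 participants will be initiated on IP" and continues: "Assuming a 20% dropout rate by the end of the study period, approximately 160 patients at the end of the study".

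Four other provisions decide how much this matters:

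- **FAS.** It requires at least one HbA1c after study treatment (SAP 6.2). The schedule of activities (Protocol 1.3) has post-baseline HbA1c only at Weeks 12 and 24.
- **Per-protocol set.** It requires completion of the 24-week treatment phase (SAP 6.3).
- **Safety set.** Protocol 9.3 and 9.4.2 assign the AE endpoints to it, meaning all patients with at least one dose. SAP Section 5 states that the planned analyses are unchanged.
- **Censoring.** SAP 18.3.2 treats patients who discontinue before 24 weeks without a GI AE as censored, and plans Kaplan-Meier plots for nausea, vomiting and diarrhoea.

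**The concern.** The same early leaver is handled in two ways. In the GI time-to-event analysis the patient contributes time at risk and is then censored. In the primary AE proportion, if the patient is in the analysis set, he or she stays in the denominator as AE-free for all 24 weeks. For any fixed set of patients, events seen before departure are a subset of those that full follow-up would show. As an estimate of 24-week risk, the crude figure can therefore only lose events to shortened follow-up. The exact interval reflects sampling error alone and is centred on the lowered figure.

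This is a primary endpoint of a safety study done to meet a marketing-authorization condition, so readers are likely to take the percentage as the 24-week risk. The plan's other adjusted analyses do not supply that risk. The exposure-adjusted incidence and the negative binomial models give rates per unit of time, and Kaplan-Meier covers three GI terms only.

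**Working it through.** **Participant flow.** Protocol 9.6: 250 × 0.8 = 200 started on drug, and 200 × 0.8 = 160 at the end. The stated figures reproduce. The documents give no AE rate, CI width or coverage, so the rest uses assumed risks.

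**Inputs.** n = 200 and dropout d = 20% (Protocol 9.6); two-sided 95% limits (SAP 7.4). Assumed: true 24-week risk p of 30, 50 or 70%; dropout unrelated to AEs.

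**Formulas.** With F(t) the probability of a first AE by week t, the expected crude proportion is q = (1 − d)·p + d·(mean of F over the dropout times). Coverage is the sum of Binomial(x; n, q) over those x whose Clopper-Pearson limits contain p. For constant hazard let H = −ln(1 − p).

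**Safety population, n = 200, dropout even over Weeks 0-24.** Mean F = 1 − p/H. At p = 50%: 1 − 0.5/0.6931 = 0.2787, so q = 0.8 × 0.5 + 0.2 × 0.2787 = 0.4557.

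**FAS, leavers before Week 12 excluded.** Even dropout puts 20 of the 40 before Week 12, so n = 180 and d = 20/180. Mean F over Weeks 12-24 = 1 − 2(√(1 − p) − (1 − p))/H. At p = 50%: 1 − 2(0.7071 − 0.5)/0.6931 = 0.4024, so q = (8/9) × 0.5 + (1/9) × 0.4024 = 0.4892.

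**FAS, all 40 leave in Weeks 12-24.** n = 200 and d = 0.2. At p = 50%: q = 0.4 + 0.2 × 0.4024 = 0.4805.

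| Setting | Crude estimate at p = 30/50/70% | Coverage of nominal 95% CI |
|---|---|---|
| Safety population, constant hazard | 27.2 / 45.6 / 64.4% | 86 / 79 / 63% |
| Safety population, front-loaded AEs (Weibull shape 0.5) | 28.2 / 47.2 / 66.7% | 92 / 90 / 84% |
| FAS, leavers before Week 12 excluded, constant hazard | 29.3 / 48.9 / 68.8% | 95.6 / 94.7 / 94.1% |
| FAS, all leave in Weeks 12-24, constant hazard | 28.7 / 48.1 / 67.8% | 93.4 / 92.9 / 90.9% |
| FAS, all 40 leave before Week 12 and are excluded (n = 160) | no truncation bias | 95% or more |
| Per-protocol set | no dropout truncation | not affected |

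With stronger front-loading (shape 0.4) the safety-population figures are 28.5/47.7/67.2%, with coverage 92.6/91.5/88.2%. For an SAE-like risk of 5% in the safety population, the bias is at most 0.5 points and coverage stays above 95%.

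**Check of the remedy.** In 4,000 simulated trials (n = 200, 20% even dropout, constant hazard), 1 minus Kaplan-Meier at Week 24 averaged 29.9/50.0/70.0%. Its complementary log-log CIs covered 95.3/94.9/94.3%.

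**The case against.** The strongest objection is the population. A reader might infer that 18.2.2 divides by all 200 treated patients, so that 79% coverage at a 50% risk describes the SAP. It does not. The section names the FAS and the per-protocol set. A patient who leaves at Week 6 normally has no post-treatment HbA1c and drops out of the FAS, and that patient is never in the per-protocol set. This stands, and it removes most of the coverage loss from the SAP as written. It does not remove the point. The protocol assigns the endpoint to the safety population. Protocol 7.2 also asks for an early-discontinuation visit where possible, but neither the schedule of activities nor the visit list in SAP 23.9 shows one. How many early leavers have an HbA1c and stay in the FAS is therefore unknown in advance.

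Other tempting readings also go too far:

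- **All 40 dropouts are counted as AE-free.** Protocol 9.6 assumes dropouts of any kind. At a 50% risk with constant hazard, about 0.2787 × 40 ≈ 11 would already have had an AE and be counted, leaving about 29. Some losses may also fall after Week 24, since the last visit is Week 28, and stopping the drug does not end follow-up (Protocol 7.1).
- **The error is always towards fewer AEs.** That is true within a fixed set of patients. Compared with all treated patients, the FAS also selects, and the direction then depends on whether the excluded early leavers had more or fewer AEs than those kept.
- **The crude figure is wrong.** The endpoint is worded as patients reporting AEs, no hypothesis is tested (Protocol 9.1), and the stated aim is adequate description. As a description of reported events the proportion is correct.

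It is also fair that the most common AEs are expected to be GI events occurring early (Protocol 2.3.1 and 4.2). This favours the front-loaded figures, and nausea, vomiting and diarrhoea already have a censored analysis.

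**Conclusion.** The point holds as a gap in the analysis. The crude proportion makes no allowance for shortened follow-up, and no planned output gives a follow-up-adjusted 24-week risk of any AE, TEAE or SAE.

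Its size depends on the population. For AE risks of 30-70% in the safety population, the understatement is 2.8 to 5.6 points under constant hazard and about 2 to 3 points if AEs come early. In the FAS as written it is about 1 point with essentially nominal coverage, rising to 1.3-2.2 points and 91-93% coverage if all dropout falls after Week 12. It is absent in the per-protocol set and negligible for SAEs near 5%.

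These figures rest on assumed AE risks, the full 20% dropout falling within 24 weeks, and dropout unrelated to AEs. They support a cheap addition to the tables. They do not support calling the SAP's FAS intervals seriously invalid.

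**What to change.** In SAP 18.2.2, keep the crude proportion and its exact CI as the description of reported events. Beside it, add the cumulative incidence at Week 24 of first AE, first TEAE and first SAE with 95% CIs, censored at last contact. Use Kaplan-Meier, or Aalen-Johansen with death as a competing event. Run these rows in the safety analysis set: in the FAS they could not recover early leavers who have already been excluded, or those patients' AEs.

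The cost is a few table rows, using a method the SAP already plans for GI events. The intervals may be slightly wider, and the estimate assumes that dropout is unrelated to AE risk, which a table footnote should state.

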18.3 Incidence of gastrointestinal (GI) AEs

18.3.1 Variables and derivations

Variables:

- All gastrointestinal (GI) AEs will be captured in the “Adverse Events” eCRF form.

Derivations:

- If the adverse event preferred terms (PT) are coded as “Nausea, Vomiting and Diarrhoea” and system organ class (SOC) are coded as “Gastrointestinal disorders” then corresponding adverse events will be considered as gastrointestinal (GI) AEs for primary analysis. Any additional PT under GI may be added as per medical review before final analysis. However, all AE terms that get coded under GI as per medical dictionary or medical review will be considered as GI for safety analysis.

18.3.2 Analyses

Population: FAS and PP

Stratification: Table: Add the strata as needed in case subjects with dose modification exceeding 20% based on enrolled population as per section 7.3:

- a. Subjects on 1.5 mg only
- b. Subjects on 0.75 mg only
- c. Subjects with any dose modification*

* Subjects who have received at least one dose of 1.5 mg and at least one dose of 0.75 mg

Statistics: The incidence of GI AEs will be summarised and a plot of prevalence by severity (mild, moderate, or severe) for nausea, vomiting, and diarrhoea over the 24-week period will be provided for the rate of GI AEs. Plot of severity with reference to time will be provided by subjects.

Three Cox proportional hazard models, each with covariates for baseline HbA1c and baseline insulin use, will be used to model the time to the first onset of nausea, vomiting, or diarrhoea TEAE,

respectively. Hazard ratio and 95% confidence interval and p-value will be presented for the covariates for the overall data. If additional analysis based of dose stratification is done, the Hazard ratio and 95% confidence interval and p-value will also be presented for dose with 1.5 mg as the reference group.

Subjects who do not experience any GI AEs during 24 weeks and discontinued before 24 weeks of period will be considered as censored.

The Kaplan Meier plot (unadjusted) will be presented for median time to first onset of nausea, vomiting, or diarrhoea TEAE, respectively along with corresponding 95% confidence interval. Y axis will represent the survival probability of the GI AEs and X axis will represent the duration in days of GI event occurred from first dose administration. Number of subjects at risk will be presented in the plot.

Additionally, all the analysis will be repeated for the below mentioned subgroups:

- age (<65 year and \geq 65 year)
- HbA1c (<8.5 and \geq 8.5)
- Sex (Female and male)
- BMI category (<27 kg/m²) and \geq 27 kg/m²)

19. Secondary endpoint**19.1 Mean change in HbA1c from baseline to Week 24****19.1.1 Variables and derivations**

Variables:

- HbA1c results

Derivations:

- HbA1c results between visit baseline visit 2 (week 0) and visit 8 (week 24) will be used.

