6.5. Dose Modification

Dose modifications are permitted only once in the following circumstances. The dose modification will be permitted only once within a maximum of 4 to 6 weeks after starting treatment with dulaglutide.

- As per common practice in India, treatment may be started with 0.75 mg of dulaglutide as combination therapy. The dose may be up titrated to 1.5 mg after a period of 2 to 4 weeks in consultation with the medical monitor. For patients who report GI AEs after starting treatment with 1.5 mg dulaglutide, the investigator may reduce the dose to 0.75 mg based on symptoms reported by patients. Treatment will be continued with 0.75 mg for 2 to 3 weeks. Thereafter, the 1.5-mg dose will be reintroduced.

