7.3 Stratifications

In general, the treatment will be presented as overall strata (i.e., Dulaglutide treatment group). However if more than 20% of the subjects undergo dose modification/downgrade or receive only 0.75 mg dose during the trial, then separate strata will be presented apart from overall: subjects with 1.5 mg only, subjects with any dose modification (at least one dose of 1.5 mg and at least 1 dose of 0.75 mg) and subjects with 0.75 mg only if they constitute more than 20% of the enrolled population. If 0.75 mg only group constitutes less than or equal to 20% of enrolled population then it can be clubbed together with the dose modified group.

Note: The dose modification may not be applicable for those who start on 0.75 mg and upgrade to 1.5 mg.

Subgroup analysis will be done on the primary, secondary, and exploratory data based on the below stratification:

- age (<65 year and \geq 65 year)
- HbA1c (<8.5 and \geq 8.5)
- Sex (Female and male)
- BMI category (<27 kg/m²) and \geq 27 kg/m²)

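### If the 20% rule adds dose strata, the GI AE dose hazard ratio in SAP 18.3.2 compares groups partly formed by the GI AE itself, which pushes it above 1 to the extent that such events lead to dose reduction

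*SAP*

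**What the plan says.** By default SAP 7.3 reports one overall dulaglutide group. Separate strata are added "if more than 20% of the subjects undergo dose modification/downgrade or receive only 0.75 mg dose during the trial". They are 1.5 mg only, "subjects with any dose modification (at least one dose of 1.5 mg and at least 1 dose of 0.75 mg"), and 0.75 mg only. The last is shown separately only if it exceeds 20% of the enrolled population; at 20% or less, "it can be clubbed together with the dose modified group". A Note adds: "The dose modification may not be applicable for those who start on 0.75 mg and upgrade to 1.5 mg".

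SAP 18.3.2 plans "Three Cox proportional hazard models, each with covariates for baseline HbA1c and baseline insulin use" for time from first dose to first nausea, vomiting or diarrhoea. It continues: "If additional analysis based of dose stratification is done", then "the Hazard ratio and 95% confidence interval and p-value will also be presented for dose with 1.5 mg as the reference group". It names no starting-dose grouping, landmark or time-varying dose, and attaches no caution. It does not define the levels of dose; the SAP 7.3 strata are the natural reading, with 1.5 mg only as reference.

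Protocol 6.5 says: "For patients who report GI AEs after starting treatment with 1.5 mg dulaglutide, the investigator may reduce the dose to 0.75 mg". The same section allows one dose change, within the first 4 to 6 weeks. Protocol 4.2 says GI effects usually occur early in therapy.

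**The concern.** Stratum membership is not known on day 0. For a patient who starts on 1.5 mg, it depends on what happens over the following weeks, and the stated reason for a reduction is the kind of event being modelled. A patient reduced for nausea is removed from the reference group because of the nausea, and counts from day 0 as a modified-group patient with an event. The reference loses cases and the comparison group gains them. Early onset and an early dose-change window put the outcome and the regrouping in the same period.

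GI AE incidence is a primary endpoint, and the primary objective covers the safety profile of both doses. A dose hazard ratio with a p-value on that endpoint will be read as a tolerability comparison, whatever its formal status.

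**Working it through.** **From the documents.** Protocol 9.6: 250 × (1 − 0.20) = 200 treated and 200 × (1 − 0.20) = 160 completing, which reproduces the stated sample size. No hazard ratio, event rate or power is stated. More than 20% of 200 means at least 41 patients.

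**Assumed, because the documents give no rates.** True dose hazard ratio 1. Nausea risk p = 0.25 in everyone. A share s of patients starts on 0.75 mg. Onset in affected patients is exponential with mean 14 days, so 1 − exp(−42/14) = 0.950 of events occur by day 42. A share q of those early cases on 1.5 mg is reduced. All 0.75 mg starters move up to 1.5 mg and count as modified, so the 0.75 mg only group is absent.

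**Closed form.** Patients reduced: d = 200(1 − s) × p × 0.950 × q. Reference risk: r1 = [200(1 − s)p − d] / [200(1 − s) − d]. Modified risk: r2 = [200sp + d] / [200s + d]. Approximate hazard ratio: ln(1 − r2) / ln(1 − r1).

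Example with s = 0.20, q = 0.10: d = 160 × 0.25 × 0.950 × 0.10 = 3.8. r1 = 36.2/156.2 = 0.232. r2 = 13.8/43.8 = 0.315. The ratio is ln(0.685)/ln(0.768) = 1.44. Fewer than four regrouped patients produce this from a true value of 1.

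| s | q = 0 | q = 5% | q = 10% | q = 20% |
|---|---|---|---|---|
| 20% | 1.00 | 1.21 | 1.44 | 1.93 |
| 25% | 1.00 | 1.17 | 1.35 | 1.76 |
| 30% | 1.00 | 1.14 | 1.30 | 1.64 |

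**Simulated Cox models, same assumptions.** 1500 trials per scenario, summarised over trials that met the 20% rule. Ranges are over s = 20–30%.

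| Reduced | Median HR, whole-trial strata | Share with p < 0.05 |
|---|---|---|
| 5% | 1.12–1.23 | 8–11% |
| 10% | 1.28–1.43 | 14–24% |
| 20% | 1.63–1.96 | 40–63% |

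The same data grouped by starting dose give 0.97–1.01, with p < 0.05 in 4–6%.

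**Variations.**
- 20% dropout, excluding patients who leave before a post-treatment HbA1c (the FAS rule): 1.15–1.20, 1.27–1.44 and 1.63–1.93.
- Up-titration cancelled after a GI AE, with the small 0.75 mg only group merged: 1.15–1.19, 1.30–1.44 and 1.65–1.95.
- Modelled symptom not always the one that led to the reduction (35% with any GI AE, one third of them with the modelled event, 25% starters): 1.12, 1.23 and 1.56, with p < 0.05 in 6%, 9% and 19%. If every GI case has the modelled event, the ratios are 1.17, 1.32 and 1.71.

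**How often the contrast is produced.** The stratum definition in SAP 7.3 makes a patient who goes from 0.75 to 1.5 mg modified; the Note says this may not apply. With such patients counted, the rule is met in 59–100% of simulated trials at 20–30% starters, but in at most 1.3% at 10% starters. With them not counted, and all starters moving up, it is met in none. If 30% start on 0.75 mg and half stay on it, that second reading gives 5–36%; if three quarters stay, 86–96%.

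**The case against.** The strongest reply is that the contrast may never appear and has little formal weight. It needs the 20% rule to be met, and the Note leans against counting up-titrators. Protocol 9.1 states no hypotheses, and the study has no comparator. All of this stands, and it makes the issue conditional and supplementary. It does not make the number correct when it is printed.

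The likely size is also modest. A footnote to Protocol Figure 6.1 refers to intractable GI effects not amenable to treatment, which points to few reductions. The three symptoms are modelled separately, so a reduction for vomiting is only partly tied to the nausea model. Both points stand, and they favour the lower end of the ranges.

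A reader might infer something stronger: that the hazard ratio could fall well below 1, or be enormous for 0.75 mg only, so that the same data support opposite conclusions. If up-titration is withheld after a GI AE and all three strata are kept, simulation does give a modified-group ratio of 0.37–0.69 at 5–10% reduced and a 0.75 mg only ratio of 11–14. But that last group has 8–12 of 200 patients (4–6%), and SAP 7.3 shows it separately only above 20%, so this is not a planned output. Once it is merged, the ratios are back above 1. Whether up-titration is withheld after a GI AE may also be answered in Figure 6.1, which is missing from the text available here, so it cannot be called a gap in the plan.

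Lastly, the remedy is partial, because the investigator chooses the starting dose. That stands and is costed under the fix.

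**Conclusion.** The concern holds, conditionally. If dose strata are added, grouping by doses received over the whole trial moves GI cases out of the 1.5 mg only reference and raises the hazard ratio to the extent that GI AEs lead to reduction. Under the stated assumptions, with the small 0.75 mg only group merged or absent, the null value is about 1.1–1.4 at 5–10% of early cases reduced and about 1.6–2.0 at 20%. It is about 1.1–1.2 at 5–10% when the modelled symptom is not always the trigger. With no GI-driven reductions there is no bias from this source. The mechanism follows from the text; the size rests entirely on assumed rates.

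Dose-split GI AE tables share the problem. It would be wrong to conclude that the primary GI endpoint as a whole is compromised: the pooled GI results and the overall Cox models do not use these strata. The conflict in SAP 7.3 over up-titrators is a separate defect, because it can decide whether the contrast is produced at all. Both should be settled before database lock.

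**What to change.** - In SAP 18.3.2, define the dose term by starting dose at Visit 2, or as a time-dependent covariate using the dose in effect before onset.
- In dose-split GI AE tables, group by starting dose, or attribute events and person-time to the dose in effect at the time.
- Label the contrast descriptive and non-randomised, and state that the investigator chooses the starting dose.
- In SAP 7.3, reconcile the Note with the stratum definition, so that one analysis rule for up-titrators governs both the 20% test and stratum membership. State whether a 0.75 mg only group of 20% or less is merged.

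The cost is SAP wording and programming. Dose by week is already needed for the per-subject dose plot in SAP 12.2. The 0.75 mg starting group may be small, with wide intervals, and GI outputs would use different groups from the other SAP tables. Confounding by choice of starting dose remains. If 0.75 mg starters had 1.5 times the nausea incidence for reasons other than dose, the starting-dose hazard ratio would still be 1.61–1.62, against 1.98–2.11 with whole-trial strata at 10% reduced. The change removes the circularity, not that confounding.
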